11.1.2. Relationship to Trial Treatment

Both Investigator and Sponsor will assess the causality of the event in relation to the IMP based on the criteria listed in the ICH E2A guidelines:

Investigators must also systematically assess the causal relationship of AEs to IMP/trial treatment (including any other non-IMPs, radiation therapy, etc.) using the following definitions. Decisive factors for assessing the causal relationship of an AE to the IMP include, but may not be limited to, temporal relationship between the AE and the IMP, known side effects of IMP, medical history, concomitant medication, course of the underlying disease, or trial procedures.

Not related: Not reasonably related to the IMP. Adverse event could not medically (pharmacologically/clinically) be attributed to the IMP under trial in this clinical trial protocol. A reasonable alternative explanation must be available. Adverse events reported as “unlikely” related and “unrelated” will be considered unrelated for reporting purposes.

Related: Reasonably related to the IMP. Adverse event could medically (pharmacologically/clinically) be attributed to the IMP under trial in this clinical trial protocol. [Table 3](#) can be used to differentiate between the AEs related to the IMP.

Adverse events reported as definitely, probably, and possibly related will be considered as “related” for reporting purposes.

Table 3 Assessment of Causality of Adverse Events

	Assessment of Causality				
	Definitely	Probably	Possibly	Unlikely	Unrelated
Clearly due to extraneous causes	N	N	N	N	Y
Reasonable temporal association with drug administration	Y	Y	Y/N	N	N
May be produced by subject clinical state, etc.	N	N	N	Y	Y
Known response pattern to IMP	Y/N	Y/N	N	N	N
Disappears or decreases on cessation or reduction in dose	Y	Y/N	N	N	N
Reappears on re-challenge (if possible)	Y	N	N	N	N

IMP=investigational medicinal product; Y=yes; N=no

11.2. Adverse Events of Special Interest

An AESI, serious or non-serious, is an AE of scientific and medical concern specific to the Sponsor's product or program for which ongoing monitoring, additional information, and rapid communication by the Investigator to the Sponsor can be appropriate. Depending on the nature of the event, rapid communication by the trial Sponsor to other parties (e.g., regulators) might also be warranted in line with Council for International Organizations of Medical Sciences standards and local regulations.

The following are considered AESIs for this trial and must be communicated by the Investigator to the Sponsor within 2 weeks following the event.

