1.3.1. Assessment of Risk: Benefit Profile

Apraglutide is a novel, synthetic, long-acting GLP-2 analog. Its main role is to increase mesenteric blood flow and to activate pro-absorptive pathways in the gut facilitating nutrient absorption. Additionally, GLP-2 enhances gut barrier function and induces proliferative and cytoprotective pathways in the small bowel. In animal models and in normal animals apraglutide has demonstrated an effect of increased intestinal weight that appears to be the result of both increased intestinal villi and diameter (as expected for a GLP2 analog), as well as increased intestinal length. Pharmaceutical class effects associated with GLP-2 analogs include possible exacerbation of the risk of malignancies, GI obstruction, gallbladder, biliary tract, and

pancreatic disease, and increased absorption of fluids leading to fluid overload in patients with underlying cardiovascular disease.

Up to June 2022, apraglutide has been investigated in healthy volunteers, patients with SBS, and renally impaired patients at doses ranging up to 56.9 mg in the single ascending dose part and doses up to 28.9 mg in the multiple ascending dose part of the Phase 1 clinical trial GYM-P3-698. The safety profile of apraglutide is mainly based on the observed events in patients with SBS at doses from 5 mg to 10 mg. At data cut off, unblinded data of 29 patients with SBS is available as well as 51 patients exposed to apraglutide or placebo. The most frequent AEs were decrease in GI stoma output, stoma complication, nausea, fatigue, injection site erythema, diarrhea, and abdominal pain. All observed Grade 3 or 4 AEs or SAEs were isolated events with the exception of device related sepsis. The only AE currently considered expected, and causally associated with exposure to apraglutide, is abdominal pain. With regards to laboratory assessment, increases in liver transaminases were observed at a higher dose (56.8 mg).

In light of the pharmaceutical class, and observations in the pre-clinical and clinical trial setting, the Sponsor has implemented appropriate assessments and risk management activities such as information in the Informed Consent Form (ICF), Investigator's Brochure and relevant regulatory documents.

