4.3. Stopping Rules

4.3.1. Trial Stopping Rules

The trial can be stopped after completion of Part 1 according to the criterion described in [Section 4.1.1](#).

If the Investigator, the Sponsor, or the Safety Medical Monitor (who reviews medical information and safety data, and consults with the site on eligibility criteria) becomes aware of conditions or events that suggest a possible hazard to subjects if the trial continues, the trial may be terminated after appropriate consultation between the relevant parties. The trial may also be terminated early at the Sponsor's discretion in the absence of such a finding.

Conditions that may warrant termination include, but are not limited to:

- The discovery of an unexpected, significant or unacceptable risk to the subjects enrolled in the trial
- Failure of the site to enroll subjects at an acceptable rate
- Enrollment and further dosing of new subjects will be interrupted if two or more subjects experience AESIs such as fluid overload, persistent abdominal pain, gall bladder, biliary and pancreatic disease of Grade 3 and above, according to the National Cancer Institute – Common Terminology Criteria for Adverse Events (NCI-CTCAE), version 5 [\[CTCAE, 2017\]](#) of moderate intensity and/or if one or more subjects experience a Grade 4 event (unless clearly not attributable to the trial drug)

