11.1.1. Intensity of Adverse Events

The intensity of AEs is graded using the NCI-CTCAE scale ([CTCAE, 2017](#)).

Where the event is not specified in the scale, then the following definitions should be used to determine mild, moderate and severe events:

- Grade 1 (Mild): the event may be noticeable to the subject. It does not usually influence daily activities, and normally does not require intervention
- Grade 2 (Moderate): the event may make the subject uncomfortable. Performance of daily activities may be influenced, and intervention may be needed
- Grade 3 (Severe): the event may cause noticeable discomfort and usually interferes with daily activities. The subject may not be able to continue in the trial, and treatment or intervention is usually needed
- Grade 4 (Life-threatening): the subject was at risk of death; this does not apply if the subject might have been at risk of death if the event was more severe
- Grade 5 (Fatal)

A mild, moderate, or severe (Grades 1–3) AE may or may not be serious. Life-threatening and fatal (Grades 4 and 5) are always serious. These terms are used to describe the intensity of a specific event. Medical judgment will be used on a case-by-case basis.

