11.3. Serious Adverse Events

An SAE is any untoward medical occurrence that at any dose:

- Results in death
- Is life-threatening
- Requires inpatient hospitalization or prolongation of existing hospitalization
- Results in persistent or significant disability/incapacity
- Is a congenital anomaly/birth defect

Medical and scientific judgement will be exercised in deciding whether reporting is appropriate in other situations, such as important medical events or reactions that may not reach the above definition but may jeopardize the subject or may require medical or surgical intervention to prevent one of the other outcomes listed in the above definition. These will also be considered serious. Examples of such events are invasive or malignant cancers, intensive treatment in an accident and emergency department or at home for allergic bronchospasm, blood dyscrasias or convulsions that do not result in hospitalization, or development of drug dependency or drug abuse.

All SAEs must be reported immediately and within a maximum of 24 hours to the CRO and/or Sponsor of the trial by using a paper version of the SAE form, which can

be emailed to [contact] or faxed. Local fax-numbers will be made available in the Investigator Site File, if email does not work.

The CRO/Sponsor will re-evaluate the SAE and queries will be raised in the eCRF or by email/fax and returned to the site, requesting clarification or follow-up information if needed. After the initial SAE report, the Investigator is required, proactively, to provide further information regarding the subject's condition. All follow-up information obtained after initially reporting the SAE, updates on the SAE, and any other new SAEs must be entered into the CRF as soon as possible as applicable, i.e., within 24 hours after new information becomes available. The Investigator must update the information as applicable in the eCRF and/or send an email to: [contact]. Local fax-numbers will be made available in the Investigator Site File, if email does not work. Serious AEs resulting in death or which are life-threatening will be reported to the Ethics Committee within 7 days.

The minimum data required for a report is:

- Subject ID
- Trial code/protocol number
- Description of SAE or SAE term
- Assessment of causality relationship to IMP
- Name and contact details of person reporting the event

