13.4.4. Data Handling

13.4.4.1. Data Collection, Data Transfer Procedure, and Data Access

The Investigator/delegate is responsible for ensuring the accuracy, completeness, and timely reporting of subject's data.

Fully validated electronic data capture will be used to collect eCRF data. The Investigator and site personnel will be trained to enter and edit the data via a secure network, with secure access features (username, password, and ID, hence an electronic password system). A complete electronic audit trail will be maintained. The Investigator/delegate will approve the data (i.e., confirm the accuracy and completeness of the data recorded) using an electronic signature (as per US 21 Code of Federal Regulations Part 11 and/or EU Annex 11).

All subjects will be recorded in the Screening and Enrollment log. Subject numbers will be allocated in chronological order for each study site.

For each subject recruited, regardless of trial treatment initiation, an eCRF must be completed and signed by the Investigator/delegate. This also applies to those subjects who fail to complete the trial.

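### The mandatory dosing interruption counts AESIs across subjects, but a non-serious Grade 3 AESI may reach the Sponsor two weeks later, and persistent abdominal pain, a named trigger, is missing from the AESI list

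*Protocol*

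**What the plan says.** **The interruption rule (Protocol 4.3.1).** "Enrollment and further dosing of new subjects will be interrupted if two or more subjects experience AESIs such as fluid overload, persistent abdominal pain", or gallbladder, biliary and pancreatic disease, at Grade 3 and above. A second limb needs only one subject with a Grade 4 event, unless that event is clearly not attributable to the drug. The bullet stands in a list of conditions that may warrant termination, but its own verb is mandatory.

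**AESI reporting (Protocol 11.2).** AESIs "must be communicated by the Investigator to the Sponsor within 2 weeks following the event". The paragraph before describes AESIs as events for which rapid communication to the Sponsor can be appropriate.

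**SAE reporting (Protocol 11.3 and 11.1.1).** "All SAEs must be reported immediately and within a maximum of 24 hours to the CRO and/or Sponsor of the trial". Section 11.1.1 adds: "Life-threatening and fatal (Grades 4 and 5) are always serious". Under the same section an event of Grade 1 to 3 can be serious or not.

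**The AESI list (Protocol 11.2.1 to 11.2.6).** Injection site reactions; gastrointestinal obstruction; gallbladder, biliary and pancreatic disease; fluid overload; malignancies; systemic hypersensitivity. Abdominal pain is not among them.

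**What is known of abdominal pain (Protocol 1.3.1).** "The only AE currently considered expected, and causally associated with exposure to apraglutide, is abdominal pain".

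**Listings (SAP 17.1.1).** AESI listings follow the investigators' own AESI reporting. SAP Table 4, which defines a further set of events of particular interest, does not include abdominal pain either.

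**The concern.** A rule that fires at the second affected subject works only if someone keeps a current count across subjects. The protocol names nobody to keep it. The one fixed deadline by which a non-serious AESI must reach the Sponsor is two weeks. Sites could comply fully with 11.2 while further subjects are dosed after the condition in 4.3.1 has been met.

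The list mismatch is a second, independent weakness. An investigator who works from 11.2 has no instruction to flag persistent abdominal pain as an AESI. Unless it is serious, it then carries no expedited report at all, although 4.3.1 counts it.

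At stake is subject safety in a group with no stated earlier exposure. Section 1.1.3 gives 108 subjects dosed so far: 74 healthy, 26 with SBS and 8 with severe renal impairment. None is described as hepatically impaired. Subjects with moderate impairment are recruited first (1.2.1).

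**Working it through.** The documents give no event rate, accrual rate or operating characteristic for the rule, so there is no plan figure to reproduce. The check is mainly a comparison of passages.

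**Step 1. Which clock applies to which trigger event**

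| Event | Route | Limit to Sponsor |
|---|---|---|
| Any Grade 4 or 5 event | Always serious (11.1.1), so 11.3 | 24 hours |
| Serious Grade 3 AESI | 11.3 | 24 hours |
| Non-serious Grade 3 AESI on the 11.2 list | 11.2 | 2 weeks |
| Non-serious Grade 3 persistent abdominal pain | Named in 4.3.1, not in 11.2 | None that is clearly assigned |

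Only the last two rows are affected.

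**Step 2. How late the trigger can be known through reports**

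Let the two qualifying events occur at times t1 ≤ t2, with permitted reporting lags L1 and L2.

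- The condition is met at t2. It is known from reports at max(t1 + L1, t2 + L2).
- Both events non-serious Grade 3 (L1 = L2 = 14 days): up to t2 + 14, a delay of up to 14 days.
- First event non-serious, second serious (L1 = 14, L2 = 1): max(t1 + 14, t2 + 1), which approaches 14 days when the events are close together. One non-serious event is enough to cause delay.
- Both on the 24-hour route: at most 1 day.

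Post-dose observation is 14±2 days (4.1.3). An AESI on the dosing day is due at the nominal end-of-trial visit, and any later AESI is due after it.

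**Step 3. Subjects dosed in the gap (illustration only)**

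Further dosings within the lag = accrual rate × lag. Accrual is an assumption.

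| Assumed subjects per week | 14-day lag (2 weeks) | 1-day lag (1/7 week) |
|---|---|---|
| 0.5 | 0.5 × 2 = 1 | 0.07 |
| 1 | 1 × 2 = 2 | 0.14 |
| 2 | 2 × 2 = 4 | 0.29 |

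**Step 4. Effect of not counting abdominal pain (illustration only)**

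For one cohort of about 8, the chance of at least two subjects with a qualifying event is 1 − (1−p)^8 − 8p(1−p)^7, where p is an assumed per-subject rate. If a share s of those events is abdominal pain and is not counted, p becomes p(1−s).

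| p | All counted | s = 25% | s = 50% |
|---|---|---|---|
| 5% | 0.057 | 0.034 | 0.016 |
| 10% | 0.187 | 0.116 | 0.057 |
| 20% | 0.497 | 0.343 | 0.187 |

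With p = 10% and all events counted: 1 − 0.430 − 0.383 = 0.187. Steps 3 and 4 show direction and possible size. They do not estimate anything for this trial.

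**Step 5. Who could notice without the report**

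Subjects stay at the CRU for the first 8 days (4.1.3), so one investigator at one CRU could see both events directly. I found no minimum interval between subjects, no scheduled cumulative AESI review and no named keeper of the count.

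**The case against.** **The rule is not tied to Sponsor receipt.** It turns on what subjects experience. At a single CRU the investigator who doses the next subject may already know of both events. This stands, and it limits the delay to those who rely on reports. It does not say who must count.

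**There are other halts.** A reader might infer that this is the only halt that protects subjects. It is not: 4.1.5 and 4.3.1 also allow termination when a hazard or doubtful safety is recognised. Those halts are discretionary and also depend on awareness. What can be said is that this is the only mandatory, count-based one.

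**The trial may have one site.** A reader might infer several sites from 13.1, 13.3 and 13.4.4.1 ("Subject numbers will be allocated in chronological order for each study site"). But 4.3.1, 8.4 and 13.8 use the singular, and 13.6 is conditional. The number is not settled.

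**Other oversight exists.** The Safety Medical Monitor reviews safety data (4.3.1), eCRF data are reviewed on an ongoing basis (13.4.5), and an external hepatologist advises on serious hepatic AESIs (4.1.7). This stands, but none of these provisions sets a deadline.

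**The affected class is narrow.** Only non-serious Grade 3 events fall in the gap. Section 11.3 also treats important medical events as serious, and section 1.3.1 describes earlier Grade 3 or 4 events as isolated, apart from device-related sepsis. This stands.

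**Section 4.3.1 itself calls persistent abdominal pain an AESI.** On that reading it counts toward the rule, and all AEs are collected anyway (11.1). But 11.2 presents its own list as the AESIs for this trial, so the two sections still disagree.

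**Conclusion.** The point holds as a mismatch between two sections. For non-serious Grade 3 AESIs, full compliance with 11.2 allows the Sponsor and the Safety Medical Monitor to learn up to 14 days late that the condition in 4.3.1 has been met, against at most one day on the SAE route. For listed AESIs the trigger is recognised late, not missed. For persistent abdominal pain it may not be recorded or reported as an AESI, unless 4.3.1 is itself read as making it one.

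The practical weight depends on the number of sites and the pace of dosing, and the documents fix neither. It is greatest with more than one site. A reader might infer that all the remaining subjects of a cohort of eight, six after two events, could be dosed within the window. That needs a dosing pace the documents do not give, so no such count is claimed here.

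The wording of the same sentence on severity ("of moderate intensity and/or if one or more subjects experience a Grade 4 event", beside Grade 3 and above) is a separate matter. It bears on this one only because 11.1.1 equates moderate with Grade 2: on that reading the class of non-serious trigger events would be wider than assumed here.

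**What to change.** Reconcile Protocol 4.3.1 with 11.2 on two matters:

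1. **Timing.** Have events that count toward the interruption rule communicated on a timeline that lets the rule work, for example through the 24-hour route already set up in 11.3. Other AESIs can stay on the two-week limit. State which role keeps the count across subjects.
2. **List.** Make the two sections agree on whether persistent abdominal pain is an AESI, and carry the answer into the eCRF so that the SAP listings follow it. The sponsor decides which list is intended.

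The change proposes no clinical threshold. It costs protocol and eCRF wording. The downside is a few faster reports through an existing channel.

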11.2.1. Injection Site Reactions

Subjects will be monitored for ISRs for at least 1 hour after IMP administration given at site, during a trial visit at the site, or longer (i.e., until the reaction stops or the subject leaves the site), as necessary. The individual symptoms of the ISR will be reported as AEs throughout the entire duration of the trial.

Data on local tolerability will be collected as an AESI. The following characteristics of ISRs will be documented:

- Pain
- Erythema
- Induration

This document is proprietary to VectivBio and for restricted circulation and access only.

- Pruritus
- Bruising

Severity (as described in **Table 4**) and duration of these features of the ISR will be collected by the site by direct observation when the IMP is administered on site.

Table 4 Grading of Severity is based on National Cancer Institute—Common Terminology Criteria for Adverse Events 5.0 in line with other Adverse Events in this trial

Pain	
Grade 1	Mild Pain
Grade 2	Moderate pain; limiting instrumental ADL
Grade 3	Severe Pain; limiting self-care ADL
Pruritus	
Grade 1	Mild, localized reaction with only topical intervention
Grade 2	Moderate with noticeable skin change from scratching (e.g., excoriation). Oral therapy indicated
Grade 3	Widespread and resulting in treatment interruption
Induration	
Grade 1	Mild induration with skin able to slide and pinch up
Grade 2	Unable to pinch up skin but still slides
Grade 3	Severe, unable to slide or pinch, potentially limiting ADL and consideration of treatment interruption
Erythema	
Grade 1	Mild, <2.5 cm
Grade 2	Moderate, 2.5–5 cm
Grade 3	>5 cm
Bruising	
Grade 1	Mild, <2.5 cm
Grade 2	Moderate, 2.5–5 cm
Grade 3	>5 cm

ADL=activity of daily living

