4.1.3. Duration of Subject Participation

The planned length of the trial is up to 42 ± 2 days (from Screening through trial completion) for each enrolled subject.

Screening period: Lasts a maximum of 28 days; starts with the full signature (subject and Investigator/delegate) of the ICF and ends with the subject's enrollment or screening failure.

Treatment period: Starts and ends with the administration of a single apaglutide dose.

Post-treatment observation period: Starts on Day 1, the day of dosing of apaglutide, and ends 14 ± 2 days after the dose of apaglutide. For the first 8 days, the subjects will remain at the CRU.

Safety follow-up period: Starts the day after the dose of apaglutide and ends 14 ± 2 days later with the EOT visit. Subjects with AEs related to the investigational medicinal product (IMP) will be followed up until resolution or until deemed unresolvable.

The subject is expected to participate in the trial for a duration of up to 14 ± 2 days.

The visit schedule and protocol-mandated procedures are performed according to the Schedule of Events ([Table 1](#)).

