4.2. Treatment Alteration and Interruption

Not applicable.

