4.3.2. Individual Stopping Rules

This is a single dose trial, therefore, there are no individual stopping rules.

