8. INVESTIGATIONAL MEDICINAL PRODUCT(S)

8.1. Dosage and Administration

All subjects will receive a single SC dose of apraglutide (5 mg). Each apraglutide treatment will be given on Day 1, within 30 minutes following a light breakfast.

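### Grade 3 injection-site pruritus in Table 4 requires treatment interruption, which cannot occur in a single-dose trial

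*Protocol*

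**What the plan says.** Protocol section 11.2.1 makes injection-site reactions an adverse event of special interest (AESI). It names five features to document (pain, erythema, induration, pruritus, bruising) and directs that their severity be collected as Table 4 describes.

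Two Grade 3 entries in Table 4 refer to stopping treatment:
- Pruritus: "Widespread and resulting in treatment interruption".
- Induration: a physical sign, followed by "potentially limiting ADL and consideration of treatment interruption".

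Elsewhere the protocol describes a design with nothing to interrupt:
- Section 8.1 gives every subject one 5 mg subcutaneous dose.
- Section 4.1.3 says of the treatment period: "Starts and ends with the administration of a single apaglutide dose".
- The section headed "4.2. Treatment Alteration and Interruption" is marked not applicable.
- Section 4.3.2 states: "This is a single dose trial, therefore, there are no individual stopping rules".

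SAP section 17.1.1 summarises events by the severity entered on the eCRF, by hepatic function group and overall.

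**The concern.** A grade should be assignable from what the assessor observes. For pruritus, the top grade in Table 4 needs a consequence that the design excludes, so an assessor who follows the table has no route to Grade 3 however severe the itching. The wording appears to be carried over from repeat dosing. Section 12.3.2.2 shows the same trait, listing adverse events that lead to dose reduction or interruption.

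Incidence, nature and severity of adverse events form a secondary endpoint (section 3.2), and local tolerability is summarised by hepatic function group. If one sign can be graded only by departing from the table, the recorded grade depends on how each assessor handles the impossible condition.

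**Working it through.** The plan states no figure to reproduce, and no sample size or error rate is involved. The check reads each Grade 3 entry in Table 4 against the single-dose design.

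**Step 1. Can interruption occur?** There is one dose (8.1), a treatment period no longer than that dose (4.1.3), an interruption section marked not applicable (4.2), and no individual stopping rules because dosing is single (4.3.2). A reaction to the injection arises once no treatment is left to interrupt.

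**Step 2. Which Grade 3 entries depend on it?**

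| Feature | Grade 3 rests on | Mentions interruption | Requires it to have happened | Reachable after one dose |
|---|---|---|---|---|
| Pain | severity and limits on self-care | no | no | yes |
| Erythema | size above 5 cm | no | no | yes |
| Bruising | size above 5 cm | no | no | yes |
| Induration | skin that neither slides nor pinches; interruption only considered | yes | no | yes, in substance |
| Pruritus | widespread extent **and** interruption as a result | yes | yes | no |

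Interruption is mentioned in 2 of 5 features and required in 1 of 5. The pruritus entry joins two conditions with *and*, and the second is an outcome. For induration, Grade 2 needs skin that remains mobile, so immobile skin does not fit Grade 2 and belongs in Grade 3 whatever is made of the interruption phrase.

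**Step 3. Does another rule in the protocol rescue pruritus?** The generic severity definitions in section 11.1.1 do not rely on interruption, but they are offered only for events that the scale does not specify, and pruritus has its own entries in Table 4. The same section's sentence on case-by-case medical judgment closes a paragraph that separates intensity from seriousness. It does not say that Table 4 may be overridden.

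**Step 4. What reaches the tables?** SAP section 17.1.1 uses severity as recorded, and treats missing severity as severe. The same widespread pruritus could therefore appear as:
- Grade 2, if the table is followed literally;
- Grade 3, if the assessor uses judgment;
- severe by imputation, if the grade is left blank.

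**Step 5. Size for one subject.** With about eight subjects per group (section 5.2), one subject is 1/8 = 0.125, or 12.5 percentage points in that group's severity summary. This holds where the pruritus is that subject's most severe event in the category being counted.

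**The case against.** The strongest case against is that little is lost. The primary endpoints are pharmacokinetic, safety is descriptive, and no hypothesis is tested. Every injection-site symptom is still reported as an adverse event with its duration, and the SAP lists all adverse events and each AESI type separately. Systemic hypersensitivity is an AESI of its own, so widespread itching that forms part of such a reaction has another route. Table 4 is captioned as based on CTCAE 5.0, and section 11.1.1 allows medical judgment, so an assessor may well record Grade 3 anyway. The documents give no rate of severe injection-site pruritus; section 1.3.1 names injection-site erythema among the frequent events, not pruritus.

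Most of this stands and limits the point to one grade label. It does not remove the contradiction, because reliance on judgment means reliance on assessors setting the written definition aside.

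A reader might infer more from Table 4 than it supports:
- **That severe injection-site reactions in general are capped at Grade 2.** They are not. Pain, erythema and bruising reach Grade 3 with no interruption element.
- **That induration is capped as well.** It is not. The physical sign separates the grades, and interruption need only be considered. The phrase is inapplicable and ambiguous, but it is not a bar.
- **That the trial stopping rule would miss a Grade 3 AESI.** Section 4.3.1 reads "Enrollment and further dosing of new subjects will be interrupted if two or more subjects experience AESIs such as", followed by examples that do not include injection-site reactions. The list is open, so they are not clearly excluded either. The Grade 3 limb needs at least two subjects, and the one-subject limb needs Grade 4, which Table 4 does not define for any feature. An effect is possible but cannot be shown.

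**Conclusion.** The point holds in a narrow form. Grade 3 injection-site pruritus is unattainable as written, for 1 of 5 features, in every subject. Grade 3 induration carries an inapplicable phrase that does not prevent its use. The consequence is a risk that a widespread, severe pruritus is recorded as Grade 2 at most and enters the severity summary unchanged, a shift of about 12.5 points in a group of eight for each affected subject.

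This assumes that assessors apply Table 4 literally and that the eCRF repeats its wording, which the documents do not show. How often it would matter is unknown. The primary pharmacokinetic analysis is untouched. It is a small defect, worth correcting because it sits in a stated grading rule that feeds a secondary safety endpoint.

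**What to change.** Reconcile Table 4 with sections 4.1.3, 4.2 and 4.3.2 by removing the treatment-interruption wording from the Grade 3 entries for pruritus and induration, so that no grade depends on an event that the design excludes.

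Removal leaves Grade 3 pruritus resting on extent alone. The sponsor should therefore confirm the remaining wording against the CTCAE 5.0 basis cited in the table's caption; no replacement threshold is proposed here. Any eCRF grading text should be aligned with the result.

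The cost is two phrases in one table, plus the eCRF text if it repeats them. Sample size, visits and planned analyses do not change.
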